### 11.5 Safety Monitoring and Early Stopping Guidelines

Safety will be monitored throughout the trial. Dose escalation will proceed according to the dose escalation scheme described in [Section 8.8.1.2](#). If more than 1 subject has a DLT during the first cycle of treatment, dose escalation will stop. If any significant safety issues arise, the sponsor will be notified and if necessary, a decision to modify or terminate the trial (or 1 of the cohorts) will be made.

All participating sites are required to provide DLT notification forms within 24 hours of learning of the event. Additionally, site teleconferences between the sponsor and all participating sites will be held approximately every 1 to 2 weeks during the dose escalation phase to discuss any suspected AEs/DLTs that have occurred at each cohort.

Safety will be reviewed by the Safety Committee, comprising a participating investigator(s), the Medical Monitor, and the sponsor's Medical Director.

The overall responsibility of the Safety Committee is to protect the ethical, welfare, and safety interests of subjects recruited into the OP-1250-001 study and to facilitate decisions for escalation and expansion cohorts.

The Safety Committee will review and assess all available safety and efficacy data collected with specific focus on the risk:benefit of continuing specific cohort(s) during the interval

	OP-1250-001	Page 93 of 111
---	-------------	----------------

observation window. The Safety Committee will meet as required to determine escalation to the next cohort and at least quarterly during dose expansion to evaluate safety and efficacy data, to identify potential treatment harm and all-cause mortality/morbidity, and to act in an advisory capacity to the sponsor.

#### **11.6 Changes in the Conduct of the Study or Planned Analyses**

Protocol modifications, except those intended to reduce immediate risk to study subjects, may only be made by Olema Pharmaceuticals. The investigator or designee must submit all protocol modifications to the IRB/EC in accordance with local requirements.

When a protocol amendment substantially alters the study design or the potential risks or burden to subjects, the ICF will be amended and approved by Olema Pharmaceuticals and the IRB/EC, and all active subjects must again provide informed consent.

## **12 ETHICS**

### **12.1 Institutional Review Board or Ethics Committee**

Prior to initiating the study, the investigator will obtain written confirmation that the IRB or EC is properly constituted and compliant with all US FDA requirements and local regulations. A copy of the confirmation from the IRB/EC will be provided to Olema Pharmaceuticals or its designee. The investigator will provide the IRB/EC with all appropriate material, including the protocol, IB, the ICF/Subject Informed Consent (PIC), and any other written information provided to the subjects, including all consent forms translated to a language other than the native language of the clinical site. The study will not be initiated until appropriate IRB/EC approval of the protocol, the ICF and all subject recruitment materials are obtained in writing by the investigator and copies are received at Olema Pharmaceuticals or its designee. The approval document should refer to the study by protocol title and Olema Pharmaceuticals, protocol number (if possible), identify the documents reviewed, and include the date of the review and approval. Appropriate reports on the progress of the study should be made to the IRB/EC or Research Ethics Board, and Olema Pharmaceuticals or its designee, by the investigator in accordance with applicable governmental regulations and in agreement with policy established by the IRB/EC and Olema Pharmaceuticals.

### **12.2 Ethical Conduct of Study**

This study will be conducted in accordance with the Declaration of Helsinki and Good Clinical Practice (GCP) according to ICH guidelines. Specifically, this study is based on adequately performed laboratory and animal experimentation; the study will be conducted under a protocol reviewed and approved by an IRB/EC; the study will be conducted by scientifically and medically qualified persons; the benefits of the study are in proportion to the risks; the rights and welfare of the subjects will be respected; the physicians conducting the study do not find the hazards to outweigh the potential benefits; and each subject, or his/her legally authorized representative will provide written, informed consent before any study-related tests or evaluations are performed.

### **12.3 Subject Information and Informed Consent**

A properly written and executed ICF, in compliance with the Declaration of Helsinki, ICH GCP and US Code of Federal Regulations for Protection of Human Subjects (21 CFR 50.25 [a,b.], CFR 50.27, and CFR Part 56, Subpart A), HIPAA (for the US only), Organic Law 15/1999 of 13 December 1999 on the Protection of Personal Data (DPA) in Spain, and other applicable local regulations, will be obtained for each subject prior to entering the subject into the study. The investigator will prepare the ICF/PIC and HIPAA authorization/Data Protection Act (DPA) and provide the documents to Olema Pharmaceuticals or its designee for approval prior to submission to the IRB/EC. Olema Pharmaceuticals and the IRB/EC must approve the documents before they are implemented. If a subject is unable to sign the ICF/PIC and HIPAA authorization/DPA, a legal representative may sign for the subject. The investigator will provide copies of the signed ICF/PIC to each subject (or the subject's legal representative) and will maintain the original in the subject's record file.

 OLEMA PHARMACEUTICALS	OP-1250-001	Page 95 of 111
---	-------------	----------------

### **13 INVESTIGATORS AND STUDY ADMINISTRATIVE STRUCTURE**

Prior to beginning the study, the investigator at each site must provide to Olema Pharmaceuticals or its designee a fully executed and signed Form FDA 1572 and a Financial Disclosure Form. All sub-investigators must be listed on Form FDA 1572. Financial Disclosure Forms must also be completed for all sub-investigators listed on the Form FDA 1572 who will be directly involved in the treatment or evaluation of research subjects in this study.

The study will be administered by and monitored by employees or representatives of Olema Pharmaceuticals. Clinical research associates will monitor each site on a periodic basis and perform verification of source documentation for each subject as well as other required review processes. Olema Pharmaceutical's designee will be responsible for the timely reporting of SAEs to appropriate regulatory authorities as required.

## 14 CASE REPORT FORMS AND SOURCE DOCUMENTS

Authorized study site personnel will complete eCRFs designed for this study according to the completion guidelines that will be provided. An eCRF is required and must be completed for each enrolled subject, with all required study data accurately recorded such that the information matches the data contained in medical records (eg, physicians' notes, nurses' notes, study site charts, or other study-specific source documents). The investigator will ensure that the eCRFs are accurate, complete, legible, and completed in a timely manner following each subject's visit (unless required earlier for SAE reporting). The investigator will ensure that source documents that are required to verify the validity and completeness of data transcribed in the eCRFs are never obliterated or destroyed. As required by the protocol, eCRFs should also be completed for those subjects who fail to complete the study (even during the screening period). If a subject withdraws from the study, the reason must be noted in the eCRF and thorough efforts should be made to clearly document outcome.

The eCRFs for this study will exist within a web-based electronic data capture (EDC) system. After the investigator or the investigator's designees (eg, research coordinators) have been appropriately trained, they will be given access to the EDC system and will enter the data required by the protocol into the EDC system. Any change of data will be made via the EDC system, with all changes tracked by the system to provide an audit trail.

The eCRF must be completed and signed by the investigator or sub-investigator (as appropriate) within a reasonable time period after data collection. This signature serves to attest that the information contained in the eCRF is true.

## 15 STUDY MONITORING AND AUDITING

Qualified individuals designated by Olema Pharmaceuticals will monitor all aspects of the study according to GCP and standard operating procedures for compliance with applicable government regulations. The investigator agrees to allow these Olema Pharmaceuticals designated monitors direct access to the clinical supplies, dispensing, and storage areas and to the clinical files, including original medical records of the study subjects, and, if requested, agrees to assist the Olema Pharmaceuticals designated monitors. The investigator and staff are responsible for being present or available for consultation during routinely scheduled site visits conducted by Olema Pharmaceuticals or its designees.

Members of Olema Pharmaceuticals GCP Compliance Department or designees may conduct an audit of a clinical site at any time during or after completion of the study. The investigator will be informed if an audit is to take place and advised as to the scope of the audit. Representatives of the FDA or other regulatory agencies may also conduct an audit of the study. If informed of such an inspection, the investigator should notify Olema Pharmaceuticals immediately. The investigator will ensure that the auditors have access to the clinical supplies, study site facilities, original source documentation, and all study files.

	OP-1250-001	Page 98 of 111
---	-------------	----------------

## 16 RETENTION OF RECORDS

The investigator must retain all study records required by Olema Pharmaceuticals and by the applicable regulations in a secure and safe facility. The investigator must notify Olema Pharmaceuticals of any change in the location, disposition, or custody of the study files. The investigator/institution must take measures to prevent accidental or premature destruction of essential documents, that is, documents that individually and collectively permit evaluation of the conduct of a study and the quality of the data produced, including paper copies of study records (eg, subject charts) as well as any original source documents that are electronic as required by applicable regulatory requirements.

All study records must be retained for at least 2 years after the last approval of a marketing application in the US or an ICH region and until (1) there are no pending or contemplated marketing applications in the US or an ICH region or (2) at least 2 years have elapsed since the formal discontinuation of clinical development of the IP. No records relating to this study should be disposed of without the written approval of Olema Pharmaceuticals. It is the responsibility of Olema Pharmaceuticals to inform the investigator/institution as to when these documents no longer need to be retained.

 OLEMA PHARMACEUTICALS	OP-1250-001	Page 99 of 111
---	-------------	----------------

## 17 DISCLOSURE OF DATA

Subject medical information obtained by this study is confidential, and disclosure to third parties other than those noted below is prohibited.

Upon the subject's permission, medical information may be given to his or her personal physician or other appropriate medical personnel responsible for his or her welfare.

Data generated by this study must be available for inspection upon request by representatives of the US FDA, national and local health authorities, Olema Pharmaceuticals, and the IRB for each study site, if appropriate.

## 18 PUBLICATION AND INFORMATION DISCLOSURE POLICY

All information provided by the sponsor and all data and information generated by the site as part of the study (other than a subject's medical records) are the sole property of Olema Pharmaceuticals.

For clinical interventional studies in subjects, Olema Pharmaceuticals will post study results on websites such as <https://clinicaltrials.gov/> and <https://eudract.ema.europa.eu/> in accordance with FDA and EU reporting rules.

Any publication or presentation of the results of this study may only be made in compliance with the provisions outlined in the executed Clinical Trial Agreement. Publication of scientific and clinical data will follow the recommendations of the International Committee of Medical Journal Editors (ICMJE), the CONSORT (Consolidated Standards of Reporting Trials) group and Good Publication Practice (GPP).

## 19 STUDY DISCONTINUATION

Both the sponsor and the investigator reserve the right to terminate the study at any time. Should this be necessary, both parties will arrange discontinuation procedures. The investigator will be responsible for notifying the relevant study site's IRB/IEC. The sponsor will be responsible for notifying the appropriate regulatory authorities. In terminating the study, the sponsor and the investigator or designee will assure that adequate consideration is given to the protection of the subjects' interests. As directed by the sponsor, all study materials must be collected and all eCRFs completed to the greatest extent possible.

## 22 APPENDICES

### 22.1 APPENDIX A: ECOG Performance Status Scale

Grade	Descriptions
0	Normal activity. Fully active, able to carry on all pre-disease performance without restriction.
1	Symptoms, but ambulatory. Restricted in physically strenuous activity, but ambulatory and able to carry out work of a light or sedentary nature (e.g., light housework, office work).
2	In bed <50% of the time. Ambulatory and capable of all self-care, but unable to carry out any work activities. Up and about more than 50% of waking hours.
3	In bed >50% of the time. Capable of only limited self-care, confined to bed or chair more than 50% of waking hours.
4	100% bedridden. Completely disabled. Cannot carry on any self-care. Totally confined to bed or chair.
5	Dead.

## 22.2 APPENDIX B: Examples of Strong CYP3A Inducers and Inhibitors to be Avoided

Strong CYP3A4 Inducers	Strong CYP3A4 Inhibitors
Apalutamide Avasimibe Carbamazepine Enzalutamide Ivosidenib Lumacaftor Mitotane Phenytoin Rifampin Rifapentine St John's Wort Extract	VIEKIRA PAK2 (Dasabuvir, Ombitasvir, Paritaprevir, and Ritonavir) Boceprevir Ceritinib Clarithromycin Cobicistat (Gs-9350) Conivaptan Danoprevir / Ritonavir Elvitegravir / Ritonavir Grapefruit/ Grapefruit Juice Idelalisib Indinavir Indinavir / Ritonavir Itraconazole Josamycin Ketoconazole LCL161 Lonafamib Lopinavir / Ritonavir Mibefradil Mifepristone Nefazodone Nelfinavir Posaconazole Ribociclib Ritonavir Saquinavir Saquinavir / Ritonavir Seville orange/ Seville orange juice Telaprevir Telithromycin Tipranavir / Ritonavir Troleandomycin Tucatinib Voriconazole

**22.3 APPENDIX C: Example of Concomitant Medications with Known Risk of QT Interval Prolongation or Increased Risk of Torsades de Pointes to be Avoided**

Concomitant Medications to Avoid
Disopyramide Dofetilide Domperidone (Non Us) Donepezil Dronedarone Levosulpiride (Non Us) Mesoridazine (Off Us Market) Methadone Moxifloxacin Ondansetron Oxaliplatin Terodiline (Non Us) Thioridazine Vandetanib

#### 22.4 APPENDIX D: Example of Concomitant Medication to be Used with Caution

CYP2C9 sensitive substrates	CYP2C8 sensitive substrates	P-gp sensitive substrates	BCRP
(S)-warfarin Tolbutamide	Daprodustat Dasabuvir Repaglinide	Digoxin Dabigatran etexilate Betrixaban Edoxaban Fexofenadine (terfenadine carboxylate) Talinolol	Rosuvastatin Sulfasalazine

## 22.5 APPENDIX E: RECIST V1.1

Disease response in target and non-target lesions will be assessed by the Investigator using RECIST v1.1 ([https://ctep.cancer.gov/protocolDevelopment/docs/recist\\_guideline.pdf](https://ctep.cancer.gov/protocolDevelopment/docs/recist_guideline.pdf)), according to the categories and criteria described in Table 14. The best overall response for each subject will be reported as the best response documented over the sequence of objective statuses recorded using the categories and criteria in Table 15.

When possible, the same qualified physician will interpret results to reduce variability.

**Table 14: Response Evaluation Criteria in Solid Tumors (RECIST v. 1.1) Guidelines for Tumor Response**

Disease Response Criteria for Target and Nontarget Lesions	
Evaluation of Target lesions	
Complete Response (CR):	Disappearance of all target lesions.
Partial Response (PR):	At least a 30% decrease in the sum of the LD of target lesions, taking as reference the baseline sum LD.
Stable Disease (SD):	Neither sufficient shrinkage to qualify for PR nor sufficient increase to qualify for PD, taking as reference the smallest sum LD since the treatment started.
Progressive Disease (PD):	At least a 20% increase in the sum of the LD of target lesions, taking as reference the smallest sum LD recorded (nadir) since the treatment started or the appearance of one or more new lesions.
Evaluation of Nontarget lesions	
Complete Response (CR):	Disappearance of all nontarget lesions and normalization of tumor marker level.
Non-CR/non-PD:	Persistence of one or more nontarget lesion(s) or/and maintenance of tumor marker level above the normal limits.
Progressive Disease (PD):	Appearance of one or more new lesions and/or unequivocal progression of existing nontarget lesions.

Source: Eisenhauer EA, Therasse P, Bogaerts J, Schwartz LH, Sargent D, Ford R, et al. New response evaluation criteria in solid tumours: revised RECIST guideline (version 1.1). Eur J Cancer 2009;45(2):228-47.

Key: LD = longest diameter.

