### 10.3 Procedures to Assess Efficacy (Biopsy and Disease Assessment)

#### 10.3.1 Radiologic Assessments

Computed tomography (with contrast) or MRI of chest, abdomen, and pelvis must be obtained within 28 days prior to the first IP dose. The same method (CT with contrast or MRI) must be used throughout the study. Subjects with brain metastasis should have MRI scans of the brain.

Radiographic assessment (and physical assessments of malignancy) should be performed at every 2 cycles starting at C3 (ie, C5, C7, C9, etc). Assessments must be performed prior to commencing treatment for that cycle. Post C9 assessment, subjects who have been determined to have obtained a clinical benefit from OP-1250 may reduce frequency of assessments to every 3 cycles (ie, C12, C15, C18, etc.) prior to commencing treatment for that cycle.

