10.3 Baseline Values

For efficacy purposes, baseline is defined as the last disease assessment conducted on or before the date of first dose of study drug.

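### Table 14 takes its PD and SD reference from sums recorded since treatment started, so target-lesion growth alone cannot be scored PD at the first (C3) scan

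*Protocol*

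**What the plan says.** Appendix E has the investigator assess response under RECIST v1.1 "according to the categories and criteria described in Table 14". In that table a new lesion counts as target-lesion PD, and so does "At least a 20% increase in the sum of the LD of target lesions". The row then fixes the comparison for that increase by "taking as reference the smallest sum LD recorded (nadir) since the treatment started". The SD row also works by "taking as reference the smallest sum LD since the treatment started". The PR row differs: "taking as reference the baseline sum LD". The table therefore separates a baseline reference from an on-treatment one.

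The timing of baseline is clear. Protocol 10.3.1 says the CT or MRI "must be obtained within 28 days prior to the first IP dose", and SAP 10.3 says that for efficacy "baseline is defined as the last disease assessment conducted on or before the date of first dose of study drug". On-treatment imaging "should be performed at every 2 cycles starting at C3", before that cycle's treatment begins, so the first scans fall at about weeks 8, 16 and 24 (C3, C5, C7).

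No readable part of either document says that the nadir includes the baseline sum, and none gives a minimum increase in millimetres. Protocol 8.11 repeats only the 20% diameter figure and its volume equivalent. SAP 10.1 refers to RECIST version 1.1 without defining PD or citing Table 14.

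**The concern.** A nadir limited to sums recorded since treatment started leaves out a scan done before the first dose. The C3 sum then has no predecessor, and a subject whose target lesions grew by half over the first two cycles is scored SD unless something else shows progression.

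PD feeds several results. SAP 10.1 discards time-point responses after the first PD and denies clinical benefit to subjects who progress before about week 24. A late PD call can therefore turn an early progressor into SD and then into clinical benefit, and CBR is the stated Phase II secondary efficacy endpoint. Scoring is also by investigators at several centers. A site that reads Table 14 literally and a site that includes baseline would score the same scans differently, and the SAP gives no rule for settling the difference.

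**Working it through.** **Inputs.** The 20% threshold and the reference wording are from Table 14, scan timing from Protocol 10.3.1, and the CBR and SD-duration rules from SAP 10.1. The lesion series are illustrative.

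**The plan's own figure.** Protocol 8.11 equates a 20% diameter increase with a 73% volume increase. 1.20³ − 1 = 0.728, so this reproduces. It confirms the threshold but not the reference.

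**The two rules.** Let S₀ be the baseline sum and S₁, S₂, S₃ the sums at C3, C5 and C7.

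- As written: PD at scan k if Sₖ ≥ 1.2 × min(S₁, …, Sₖ₋₁). At k = 1 this set is empty. Taking S₁ as its own nadir does not help, since S₁ ≥ 1.2 × S₁ is never true.
- Baseline included: PD at scan k if Sₖ ≥ 1.2 × min(S₀, …, Sₖ₋₁).

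| S₀, S₁, S₂, S₃ (mm) | Baseline included | As written |
|---|---|---|
| 50, 65, 72, 80 | 65/50 = 1.30, PD at C3 | 72/65 = 1.11; 80/65 = 1.23, PD at C7 |
| 40, 50, 55, 58 | 50/40 = 1.25, PD at C3 | 55/50 = 1.10; 58/50 = 1.16, not PD through C7 |
| 40, 60, 60, 60 | 60/40 = 1.50, PD at C3 | 60/60 = 1.00 twice, not PD through C7 |

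**Steady growth at rate g per 8 weeks.** PD by week 16 needs (1 + g)² ≥ 1.2, that is g ≥ 9.5%, with baseline included. As written it needs 1 + g ≥ 1.2, that is g ≥ 20%. Growth between these rates passes week 16 as SD.

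**CBR.** Cycle 7 Day 1 is day 6 × 28 + 1 = 169, so 24 weeks have then elapsed. An SD at C3 (about day 56) exceeds the SAP's 42-day minimum. The second and third subjects, if still on treatment at 24 weeks, meet the CBR definition. For the first subject it depends on the C7 scan date and the end-of-treatment date, because the SAP's cut-off for disqualifying PD is 7 days before Cycle 7 Day 1.

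**ORR.** PR requires Sₖ ≤ 0.7 × S₀ under either rule, so the PD reference rarely matters to it.

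**No absolute minimum.** 20% of 10 mm is 2 mm and 20% of 15 mm is 3 mm; Table 14 scores either as PD. To see how this interacts with the reference, I simulated one unchanged 15 mm lesion with independent normal measurement error at baseline, C3, C5 and C7 (400,000 draws per setting). The error SDs are assumptions.

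| Assumed SD | False PD by C7, as written | Baseline included |
|---|---|---|
| 0.5 mm | under 1% | under 1% |
| 1.0 mm | about 7% | about 13% |
| 1.5 mm | about 23% | about 37% |

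Including baseline adds a comparison and lowers the running minimum, so noise-driven PD in small sums rises.

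**The case against.** The best reply is that nobody would read the row this way. It makes the target-lesion PD criterion empty at C3, yet the plan schedules that scan as a response assessment. Appendix E also links the RECIST 1.1 guideline, and the SAP invokes RECIST 1.1 directly. This shows that the literal result was probably not intended. It does not remove the problem: Appendix E makes Table 14 the criteria to apply, the PR row shows that the table names baseline when it means baseline, and no readable text corrects the PD and SD rows.

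Second, early growth may come to light in other ways. This stands in part. New lesions and unequivocal non-target progression still give PD at C3. CBR also requires 24 weeks on treatment, and the investigator may stop treatment on other grounds. Such a stop does not fully repair CBR, however: SAP 8.6 excludes subjects treated for less than 24 weeks without radiographic progression, so an early progressor whose growth was not scored PD leaves the denominator instead of counting as a failure.

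Third, the missing absolute minimum rests on little. This largely stands. The documents do not show that the cited source contains a minimum, the error SDs are assumed, and the effect is confined to small sums. Using one imaging method throughout and, where possible, the same reading physician limits measurement error. It is therefore only a secondary point.

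**Conclusion.** The wording of the PD and SD reference needs correcting. As written, PD based on target lesions alone cannot be called at C3. The delay is one scan (8 weeks) for steady growth of 20% or more per 8 weeks, two scans in the 50/65/72/80 mm series, and beyond C7 in the 40/50/55/58 mm series. The likely direction is toward more SD and a higher CBR. With an illustrative denominator of 50, each reclassified subject moves CBR by 1/50, or 2 percentage points. How many subjects would be affected cannot be computed, because no lesion-size or growth distribution is given. The conclusion assumes a literal reading of Table 14. Protocol 10.3.2 is largely illegible in the copy reviewed, so a clarification there cannot be ruled out.

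Four stronger readings are not supported:

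- That all early growth is scored SD: new lesions and non-target progression still count.
- That slowing growth is never called by week 24: the 50/65/72/80 mm series is called at C7.
- That the primary ORR is materially biased by the reference: PR is measured from baseline.
- That Table 14 omits a required millimetre minimum, or that the baseline-included false-PD rates describe the written rule: the documents show no such minimum, and the written rule gives the lower rates.

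**What to change.** In the PD and SD rows of Table 14, state that for response scoring the reference is the smallest sum on study, including the baseline sum, so that the table agrees with the RECIST 1.1 criteria that the protocol and SAP invoke. Put the same definition in SAP 10.1 for time-point responses and for the progression check in CBR. In the same edit, check whether the source cited under Table 14 sets a minimum absolute increase, and state the answer either way. The two should be settled together, since including baseline alone raises noise-driven PD in small sums.

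PD is also a ground for ending treatment in Protocol 8.3.3 and 8.11. The sponsor should reconcile those passages with the revised table; no treatment rule is proposed here.

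The cost is a few phrases in Appendix E, a sentence in the SAP, and a programmed check on target-lesion sums already needed for the SAP 10.2 waterfall plot. No new scans are required.
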